5.6 Description of Data Collection

Definition of Study Assessments

All patients will be closely monitored for safety and tolerability throughout the study. Patients will continue dosing until they experience intolerable AE's, discharge from hospital, patient withdrawal or termination of the study. Subjects may be discontinued from study treatment in the following situations: 1) subject has decided to withdrawal from the study, 2) Intolerable adverse events, 3) mechanical ventilation (e.g. intubation, high-flow O₂ Bi-PAP or AIRVO) or death, 4) pregnancy, or 5) severe noncompliance. The schedule of activities is listed in section C.

Medical History

Medical history and demographics will be collected at screening. Medical history will include other significant co-morbidities, previous surgeries, history of hypertension, chronic obstructive lung disease, asthma, diabetes, cancer, previous chemotherapy and outcomes, prior immunosuppressive drug therapy including

Protocol Title: Duvelisib Ameliorates Manifestations of Pneumonia in Established Novel Coronavirus Infection (DAMPEN-CI)

steroids, use of tobacco, alcohol and recreational drugs and any known toxin exposure. Demographics data will include age, sex and self-identified race/ethnicity.

Performance Status

The ECOG performance status will be assessed at screening and on days 1 [baseline, prior to study drug], 8, 15, and 29.

Physical Exam

Physical exam will include focused examination of body systems, including assessment of ECOG performance status, weight, heart, lungs, abdomen, skin and nervous system. A targeted physical exam will be performed on screening and on days 1 [baseline, prior to study drug], 8, 15, and 29.

Clinical Assessments

Vital signs will be recorded daily including maximal and minimal blood pressure, heart rate, temperature, oxygen saturation. Daily weights will be recorded. The maximum level of supplemental oxygen delivered in each 24-hour period will be recorded. Results from imaging studies of the lung ordered as part of the standard-of-care management of COVID-19 patients will be extracted from the electronic medical record and entered into case report forms. Positive results from microbiological tests of blood, sputum, and bronchial lavage ordered as part of the standard-of-care management of COVID-19 patients will be extracted from the electronic medical record and entered into case report forms.

Clinical Laboratory Data

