15.1 Statistical considerations

The proportion of patients that did not require mechanical ventilation or die within 29 days of randomization will be recorded as a preliminary assessment of the efficacy of duvelisib in this setting.

Definition of subjects evaluable for efficacy response

Subjects who completed screening and enrollment procedure and who are randomized to receive duvelisib/placebo will be evaluable for efficacy endpoints on an intent-to-treat basis.

Definition of NIAID scale

The clinical response to study drug is defined as the first day on which the subject satisfies the criteria of a score of 5 or greater in the following categories from the NIAID ordinal scale. The NIAID ordinal scale is an assessment of the clinical status at the first assessment on a given study day. The scale is as follows: 1) Death; 2) Hospitalized, on invasive mechanical ventilation or extracorporeal membrane oxygenation (ECMO); 3) Hospitalized, on non-invasive ventilation or high flow oxygen devices; 4) Hospitalized, requiring supplemental oxygen; 5) Hospitalized, not requiring supplemental oxygen - requiring ongoing medical care (COVID-19 related or otherwise); 6) Hospitalized, not requiring supplemental oxygen - no longer requires ongoing medical care; 7) Not hospitalized, limitation on activities and/or requiring home oxygen; 8) Not hospitalized, no limitations on activities.

Definition of the primary efficacy endpoint

The proportion of patients who do not require mechanical ventilation (e.g. intubation, high-flow O₂ Bi-PAP or AIRVO) and who survive to 4 weeks after randomization will be used as the primary measure of efficacy.

Study design

This is a randomized placebo-controlled double blind/double masked phase 2 study to explore the efficacy of exposure to a PI3K inhibitor in patients with severe COVID-19. Subjects who are randomized to receive duvelisib or placebo will be evaluable for the primary and secondary efficacy analyses. All subjects with any exposure to duvelisib will be evaluable for toxicity (please see section 13.3 on grading of toxicities). A total of 80 subjects will be planned for analysis of the primary and secondary endpoints. We estimate that five subjects will be enrolled every month. One interim analysis is planned upon 50% (n=40) of subjects enrolled, which allows us the

Protocol Title: Duvelisib Ameliorates Manifestations of Pneumonia in Established Novel Coronavirus Infection (DAMPEN-CI)

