opportunity to stop the trial early due to futility or safety concerns. The only groups that will have access to unblinded interim data: (a) an independent data monitoring committee (IDMC); and (b) an independent statistical team whose role will be to generate the reports to be reviewed by the IDMC. The responsibility of any data-informed recommendations regarding continuing/stopping the study or modifying the study design/protocol be restricted to the IDMC.

Power Calculation

The reported incidence of death or mechanical intubation for patients with severe COVID-19 is approximately 40% (1). Local experience with COVID-19 patients at the Emory hospitals is consistent with this estimate, as 29% of all SARS-CoV-2 positive patients (n=800) are admitted to the ICU with COVID-19, and that 22% of all admitted patients are intubated, and 37% of intubated patients die in hospital. A favorable and clinically significant result from treatment with duvelisib in high-risk COVID-19 patients would be to reduce the composite incidence of death/mechanical ventilation from 40% to 15%. A sample size of 40 subjects for each treatment group will have >80% power to detect a 25% absolute reduction in the proportion of subjects who experience death or mechanical ventilation, comparing a predicted proportion of 40% death or intubation in the control arm to 15% death or intubation in the experimental arm receiving duvelisib treatment. The calculation is based on 10% type 1 error rate and two-sided Mantel-Haenszel test with one planned interim analysis when approximately 50% of sample enrolled (N=20/treatment). For

Analysis of Primary Endpoints

Analysis of the primary end-point will be based upon an intent-to-treat analysis of all subjects who are randomized to receive duvelisib/placebo. The primary endpoint is the proportion of patients who will require mechanical ventilation or experiencing death within 4-weeks (29 days) after randomization, which will be estimated with the corresponding 95% Clopper-Pearson confidence interval for the two arms separately. Fisher's Exact test will be used to test the difference between the two arms. In addition, a logistic regression will be used to estimate the odd ratio between the two arms controlling for the baseline covariates for an improved precision of the estimation (30).

Analysis of Secondary Endpoints

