Summary statistics and frequencies for the following characteristics will be described by randomized arms: ECOG, Race, Ethnicity, Age, Sex, Body mass index (BMI), Medical history of hypertension, diabetes, asthma, chronic obstructive pulmonary disease, History of and treatment for cancer, History of coronary artery disease (prior MI, CABG, coronary artery stent, or medical management), History of prior pulmonary infections (TB, pneumonia, influenza), Allergies

Subgroup analyses

None

15.2 Data/specimens:

Source Documents

Source data is all information, original records of clinical findings, observations, or other activities in a clinical trial necessary for the reconstruction and evaluation of the trial. Examples include medical records (hospital records, office charts), laboratory results, imaging scans and reports, EKGs, patient diaries, videos, photographs, pharmacy dispensing, and other records, investigator or patient completed questionnaires involved in the clinical trial.

Case Report Forms

The case report form (CRF) will be the primary data collection instrument for the study. All data requested on the CRF will be recorded and all entries will be recorded into an electronic data capture system by authorized personnel. The principal investigator is responsible for assuring that the data entered into the CRF are complete, accurate and that entries are updated in a timely fashion. Data will be entered in the clinical research data management system – REDCap - per Winship SOP 4.2 Data Completion Metrics. REDCap will be used to record all study related information and data for all registered subjects, including their assigned patient ID. All data submitted must be accompanied by supporting source documents, where applicable and as outlined in the protocol-specific monitoring plan. Data completion will be reviewed monthly. In situations where there are significant delays of data completion, the Associate Director of Clinical Research or the Director of Clinical Trials may temporarily suspend enrollment. All data must be entered in the timeframe required at each site, but no later than 30 days following registration and each visit completion. All queries are to be resolved within 4 weeks of issue. The coordinating center multi-site coordinator will provide REDCap training and request access to the appropriate staff at the participating site.

Procedures to Ensure Capturing Data for the Primary End-point

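### The primary test is an unadjusted Fisher's exact test, although power was computed for a Mantel-Haenszel test and baseline oxygen need, which could stratify that test, is recorded but not used

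*Combined protocol and SAP*

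**What the plan says.** - **Primary test** (Section 15.1, Analysis of Primary Endpoints): "Fisher's Exact test will be used to test the difference between the two arms". No stratification or adjustment is attached to it.
- **Adjusted analysis** (same paragraph): a logistic regression is added, "controlling for the baseline covariates for an improved precision of the estimation". No covariate is named.
- **Power** (Section 15.1, Power Calculation): "A sample size of 40 subjects for each treatment group will have >80% power", "comparing a predicted proportion of 40% death or intubation in the control arm to 15% death or intubation in the experimental arm". The stated basis is a 10% type I error rate, a two-sided Mantel-Haenszel test and one interim look at half the sample.
- **Oxygen data**: Section 5.6 (Clinical Assessments) says "The maximum level of supplemental oxygen delivered in each 24-hour period will be recorded". Section 5.5 lists the oxygen requirement among treatment-phase procedures. For the secondary recovery endpoint, Section 15.1 says "The NIAID ordinal scale is an assessment of the clinical status at the first assessment on a given study day".
- **Prognosis**: Section 3.1 names declining oxygenation among the settings of poor prognosis, without an effect size.
- **Baseline table** (Section 15.1, Demographics and Baseline Characteristics): "Summary statistics and frequencies for the following characteristics will be described by randomized arms". The list covers ECOG status, demographics, BMI, comorbidities, prior lung infections and allergies. It has no oxygen support, saturation or NIAID item.
- **Randomization** (Sections 1.2 and 11): stratified by study site only.

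**The concern.** Two things do not fit together. First, the test that carries the primary conclusion is not the test for which power was claimed, and Fisher's exact test is conservative at this sample size.

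Second, the primary event is escalation of respiratory support (intubation, high-flow oxygen, Bi-PAP or AIRVO) or death. Patients already on those devices are excluded at entry, so how much oxygen a patient needs at randomization is an obvious candidate predictor. The plan collects the information but uses it neither to balance the arms, nor to sharpen the primary test, nor to describe the arms.

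At stake are several points of power in a trial of 80, and the reader's ability to see whether arms of 40 started with similar oxygen need.

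**Working it through.** **Inputs.** From Section 15.1: n = 40 per arm, p1 = 0.40, p2 = 0.15, two-sided alpha 0.10 (z = 1.645). The documents give neither the distribution of baseline oxygen support nor its association with outcome. Both are assumed below and varied.

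**1. Reproduce the plan's power.**
- Pooled rate 0.275, so SE0 = sqrt(0.275 × 0.725 × 2/40) = 0.0998.
- SE1 = sqrt(0.24/40 + 0.1275/40) = 0.0959.
- Power = Φ((0.25 − 1.645 × 0.0998)/0.0959) = Φ(0.895) = 81.5%.
- Exact binomial enumeration of the unstratified Mantel-Haenszel test: 82.2%.
- With the O'Brien-Fleming final critical value 1.678, which matches the plan's interim boundary (1.678 × sqrt 2 = 2.373): 80.5% by formula, 80.8% exact.

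The claim of more than 80% therefore holds for the Mantel-Haenszel test.

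**2. Power of the test actually named.** The same enumeration for Fisher's exact test gives 75.5% at 0.10, and 73.7% at the O'Brien-Fleming final level of 0.0934. The reason is conservatism. At common event rates of 15%, 27.5% and 40%, Fisher's true type I error is 5.2%, 6.1% and 5.6%, against 9.9%, 10.1% and 9.0% for Mantel-Haenszel. The gap in power is 82.2 − 75.5 = 6.7 points and needs no assumption about oxygen.

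**3. What stratifying on oxygen adds.** In simulated trials the marginal rates were held at 40% and 15%. Event odds rose by a fixed odds ratio per oxygen level, and a stratified Mantel-Haenszel test without continuity correction was applied at two-sided 0.10.

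| Baseline oxygen (assumed) | No association | OR 2 | OR 3 | OR 5 |
|---|---|---|---|---|
| Two levels, higher level in 30-90% of patients | 81-82% | 82-83% | 83-84% | 83-85% |
| Three levels, 30/40/30%, OR per level | 81% | 83% | 85% | 88% |

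Type I error of the stratified test was about 10% throughout. Against the unstratified 82.2%, oxygen itself adds about 0-3 points with two levels and 1-6 with three. If it is unrelated to outcome, the cost is under 1 point. The low end with two levels occurs when 90% of patients share one level.

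The top three-level figure needs a steep gradient. An OR of 5 per level is 5 × 5 = 25 between the extremes, with control-arm event rates of about 10%, 37% and 74% (check: 0.3 × 10 + 0.4 × 37 + 0.3 × 74 = 40%).

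**4. Chance imbalance.** Nothing in the design balances oxygen need. For a binary factor and independent arms of 40, the chance of a difference of at least 6 patients (15 points) is 18% at 30% or 70% prevalence and 22% at 50%.

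**5. Room for covariates.** Expected events are 40 × 0.40 + 40 × 0.15 = 16 + 6 = 22. Treatment, a two-level oxygen term and a linear age term use three coefficients, about 22/3 = 7 events each.

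**The case against.** An unadjusted test under 1:1 randomization is valid. Its error rate already allows for chance imbalance, the plan calls the result a preliminary efficacy assessment, and an adjusted analysis is planned. This stands: the point concerns efficiency and description, and the planned primary test is not biased.

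The oxygen gain rests on assumed prognostic strength. This also stands. A reader might infer that leaving oxygen out is the main source of lost power; the calculations do not support that. Most of the shortfall comes from using Fisher, and oxygen adds as much as 5 or 6 points only under a very steep gradient.

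A reader might also infer that the logistic model is left with the listed baseline characteristics, that these are weaker predictors, and that fitting about 14 of them to 22 events would distort the odds ratio. The documents do not support this. The baseline list is introduced for description only, no covariates are named for the model, and oxygen is not excluded from it. Age and sex are on the list, and Section 3.3 names age and male sex as risk factors for death. What can be said is that the covariate set is unspecified and the event count allows only a short one.

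Finally, oxygen support is not strictly the entry value of the primary outcome. The endpoint is binary, and the NIAID scale serves time to recovery. Because of the entry exclusions, baseline NIAID status is in effect category 4 or 5. Three levels therefore need a cut-point on recorded oxygen amount, which the plan does not give. Nor does it define a pre-dose value.

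**Conclusion.** The point holds. The named primary test has about 75.5% power where the plan claims more than 80%, and about 7 points are recovered by using the test family assumed for power. Stratifying that test on baseline oxygen brings power to about 82-85% with two levels (OR 2-5) or 83-88% with three (30/40/30%, OR 2-5 per level). That is a total gain over Fisher of roughly 6 to 13 points. The Fisher figure and the first 7 points follow from the plan's own inputs. The oxygen contribution depends on prevalences and odds ratios that the documents do not supply. The absence of oxygen support from the baseline table is a plain omission whatever its prognostic strength.

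**What to change.** 1. Define a pre-dose oxygen-support value. The Day 1 24-hour maximum will not do, since it may include time after the first dose. The first NIAID assessment on Day 1 could give two levels (on supplemental oxygen or not) if it is confirmed to precede dosing. Use three levels only if the recorded oxygen amount supports a cut-point fixed before unblinding.
2. Make the primary comparison a two-sided Mantel-Haenszel test stratified by this value. Keep Fisher's exact test as a sensitivity analysis.
3. State how study site, the randomization stratum, is handled. Fully crossing site with oxygen level in 80 patients could leave sparse strata, so specify a pooling rule or give the reason for leaving site out.
4. Add baseline oxygen support to the baseline characteristics table.
5. Limit the logistic model to treatment, baseline oxygen and age, and name these terms in the plan.

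The cost is mainly analysis-plan wording, plus a check that a pre-dose oxygen value can be identified in the recorded data. The statistical downside is under 1 point of power relative to an unstratified Mantel-Haenszel test if oxygen proves unrelated to outcome.

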To compare the incidence of mechanical ventilation or death in subjects with severe COVID-19 given placebo or oral duvelisib.	The primary end-point is a composite endpoint of mechanical ventilation or death within 4 weeks of randomization.
Secondary	
Secondary Objectives are to compare the duvelisib cohort to the placebo cohort with respect to:
 
1) Days to recovery as assessed by ACTT endpoints as the time to recovery (Day 1 through Day 29) to satisfy a score of ≥ 5 from the following eight categories from the NIAID ordinal scale. The scale is as follows: 1. Death; 2. Hospitalized, on invasive mechanical ventilation or extracorporeal membrane oxygenation (ECMO); 3. Hospitalized, on non-invasive ventilation or high flow oxygen devices; 4. Hospitalized, requiring supplemental oxygen; 5. Hospitalized, not requiring supplemental oxygen - requiring ongoing medical care (COVID-19 related or otherwise); 6. Hospitalized, not requiring supplemental oxygen - no longer requires ongoing medical care; 7. Not hospitalized, limitation on activities and/or requiring home oxygen; 8. Not hospitalized, no limitations on activities.2) Duration of hospitalization3) Death within 29 days of randomization4) ICU transfer within 29 days of randomization5) ECOG performance status at day 15 and 29 of randomization6) Incidence of grade III-V adverse events or SAEs (as defined by CTCAE version 5)7) Documented secondary bacterial or viral infection within 29 days of randomization.8) Mean frequencies of Th1 and Th17 T cells in blood mononuclear cells at 1, 2 and 4 weeks9) Mean levels of inflammatory serum biomarkers at 1, 2 and 4 weeks10) Gene expression profiles of T cells at 1, 2 and 4 weeks

OBJECTIVES	ENDPOINTS
11) Median titers of IgG antibodies to SARS-CoV-2 at 4 weeks 12) Survival at day 50-60 after randomization	

3. Background

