- EKG as ordered by attending physician
- Labs: Complete Blood Count (includes hemoglobin, platelets, and white blood cell count with differential), Comprehensive metabolic panel (includes sodium, potassium, chloride, creatinine, AST, ALT, total bilirubin, and alkaline phosphatase), ferritin, D-dimer, CRP, troponin (abstract from SOC labs daily or as available), Thyroid Stimulating Hormone (TSH, Day 29)
- Immune phenotyping of leukocytes (days 1, 8, 15, and 29)
- Whole blood for RNA – gene expression analyses (days 1, 8, 15, and 29)
- Mononuclear cells for mass cytometry (CyTOF) (days 1, 8, 15, and 29)
- Plasma for cytokine/chemokine analyses (days 1, 8, 15, and 29)
- Serum for antibodies to SARS-CoV-2 (screening and 29)

Follow-up Phase:

- Survival status on day 50 - 60

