Blood samples for chemistry, hematology, viral serologies, leukocyte immunophenotyping and pregnancy (for pre-menopausal patients) will be analyzed at Emory or secondary site clinical laboratories. The chemistry panel will include sodium, potassium, chloride, bicarbonate, glucose, BUN, AST, ALT, total bilirubin, total protein, ferritin, D-dimer, CRP will be tested at screening and on days 1, 8, 15, and 29. TSH will be tested at screening and at day 29. Hematology panel includes complete blood count, including white blood cell count with differential (neutrophils, lymphocytes, eosinophils, basophils), red blood cell count, hemoglobin, hematocrit and platelet count will be tested at screening and days 1, 8, 15, and 29. Hepatitis viral serologies will be tested at screening if a patient has a prior history of treated hepatitis B or C, and include:

- Hepatitis B Panel (HBsAg, HBsAb, HBcAb and HBV DNA PCR)
- Hepatitis C Panel (HCV Ab and HCV PCR)

Correlative Laboratory Data

- SARS-CoV-2 RT-PCR test from nasopharyngeal swabs will be ordered at screening [baseline, prior to study drug]. Results are returned as positive or negative, with Ct values for positive tests. Note: saliva SARS-CoV-2 PCR test will be added once available.
- Leukocyte immunophenotyping (via flow cytometry/fluorescence-activated cell sorting) will be done at days 1, 8, 15, and 29. This will determine the amount of B/T/NK cells and more specifically, the phenotypes and frequencies of these immune cell populations pre and post duvelisib exposure (Th1 and Th17 T cells).
- Mononuclear cells collected at days 1, 8, 15, and 29 will be stored for CyTOF analyses for more in-depth immune-phenotyping in follow-up studies.
- Blood cells collected at days 1, 8, 15, and 29 will also be collected in RNA stabilization tubes for immunological gene expression analyses.

Protocol Title: Duvelisib Ameliorates Manifestations of Pneumonia in Established Novel Coronavirus Infection (DAMPEN-CI)

- Mean levels of inflammatory serum biomarkers will be measured by ELISA at day 1 [baseline, prior to study drug], during and following 2 weeks of study drug exposure in each cohort, using samples at days 1, 8, 15, and 29
- Median titers of neutralizing antibodies to SARS-CoV-2 will be determined at days 1 and 29.

6. Data and Specimen Banking

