Evaluable subjects will be all subjects who were randomized to receive duvelisib or placebo. The definition of secondary endpoints are listed in section 2. The descriptive statistics will mainly be applied to all secondary endpoints by treatment arms separately, such as frequency and percentage for categorical endpoints and mean, median, and standard deviation for numerical endpoints. They will be compared between treatment arms by Fisher's Exact test for categorical endpoints and Wilcoxon Rank-Sum test for numerical endpoints. For biomarkers measured repeated over time, generalized estimating equation (GEE) model will be used to test the difference in change pattern over time by two treatment groups using a nonlinear model. P-value will be adjusted for multiple comparison if necessary. Time to recovery is as the days from randomization to reach the desired NIAID ordinal scale ≥ 5 , a log-rank test will be used to compare the difference between the two arms. Survival rate at day 50 - 60 will be estimated by Kaplan-Meier method with log-rank test.

Interim Analysis for futility

The responsibility of any data-informed recommendations regarding continuing/stopping the study or modifying the study design/protocol be restricted to the independent data monitoring committee (IDMC), which is a part of the Winship data safety monitoring committee (DSMC). Upon 20 enrolled for each arm, an interim analysis will be carried out by two-sided Mantel-Haenszel test. O'Brien-Fleming boundary for futility is 2.373 on the Z score (equivalently: 0.991 on the fixed sample p-value scale). The trial may be terminated due to futility, or

Protocol Title: Duvelisib Ameliorates Manifestations of Pneumonia in Established Novel Coronavirus Infection (DAMPEN-CI)

following review by the IDMC of clinical and laboratory immune-monitoring data. Otherwise, the trial will continue enrolling patients until all 80 patients enrolled.

Stopping Rule for Safety

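### The 4-week SARS-CoV-2 IgG titre is compared by an unadjusted Wilcoxon test although a pre-dose titre is collected; this gives up precision but does not make the test invalid

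*Combined protocol and SAP*

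**What the plan says.** **Test.** Section 15.1, Analysis of Secondary Endpoints, is mainly descriptive. For between-arm comparisons it names Fisher's "Exact test for categorical endpoints and Wilcoxon Rank-Sum test for numerical endpoints". No covariate is mentioned.

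**Repeated biomarkers.** The same paragraph then treats these separately: "For biomarkers measured repeated over time, generalized estimating equation (GEE) model will be used to test the difference in change pattern over time".

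**Antibody endpoint.** Section 2 lists "Median titers of IgG antibodies to SARS-CoV-2 at 4 weeks", which is one post-baseline time point.

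**Antibody sampling.** The schedule in section 1.2 marks anti-SARS-CoV-2 IgG on Day 1 and Day 29. Section 5.5 puts Covid-19 IgG among the screening labs and later lists "Serum for antibodies to SARS-CoV-2 (screening and 29". Section 5.6 states "Median titers of neutralizing antibodies to SARS-CoV-2 will be determined at days 1 and 29". On every version an antibody sample from screening or Day 1 exists.

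**Other laboratory endpoints.** Section 2 also lists "Mean frequencies of Th1 and Th17 T cells in blood mononuclear cells at 1, 2 and 4 weeks" and "Mean levels of inflammatory serum biomarkers at 1, 2 and 4 weeks". Section 5.6 samples both on Days 1, 8, 15 and 29.

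**Adjustment elsewhere.** For the primary endpoint, section 15.1 adds a logistic regression with baseline covariates, expressly to gain precision. Nothing similar is named for the titre.

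**The concern.** Patients may enter at different stages of their antibody response. If so, part of the spread in 4-week titres was already present before the first dose. A test on the 4-week values alone treats that spread as noise, although the measurement that could remove it is already in the protocol.

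The titre matters to the design. The synopsis counts the IgG response among the key secondary endpoints, and section 5.1 gives possible preservation of humoral responses as a reason for limiting exposure. There are at most 40 patients per arm. Section 15.1 analyses secondary endpoints on observed cases only, so deaths and missed samples will reduce that number. What is at stake is the ability to detect, or reasonably rule out, an effect of duvelisib on antibody formation.

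**Working it through.** **The plan's own figure.** The documents state no power, SD, effect size or baseline correlation for the titre. Their only power statement is for the primary endpoint: 40 per arm, 40% against 15%, two-sided 10%, more than 80% power. It reproduces. With pooled proportion 0.275, z = (0.25√40 − 1.645·√(2·0.275·0.725)) / √(0.4·0.6 + 0.15·0.85) = (1.581 − 1.039)/0.606 = 0.895, so power is 81.5%. It says nothing about the titre.

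**Inputs for the titre.**
- From the documents: 40 per arm (section 15.1) and 1:1 allocation (section 1.2).
- Assumed: approximately normal log10 titres, equal SD at both times, a two-sided 10% level (the documents state this only for the primary power calculation), and ρ from 0.1 to 0.7.

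**Step 1: Wilcoxon.** Under normality its efficiency relative to the t-test is 3/π. The difference detectable with 80% power is (1.645 + 0.842)·√(2/40)/√(3/π) = 0.556/0.977 = 0.57 SD. With 30 and 20 per arm it is 0.66 and 0.81 SD.

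**Step 2: ANCOVA.** The variance is multiplied by 1 − ρ². The equivalent unadjusted sample size is 40/(1 − ρ²), and the detectable difference is 0.556·√(1 − ρ²).

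| Assumed ρ | 1 − ρ² | 40 per arm is worth | Detectable (SD) | Power at 0.57 SD |
|---|---|---|---|---|
| 0.1 | 0.99 | 40.4 | 0.55 | 82% |
| 0.3 | 0.91 | 44.0 | 0.53 | 85% |
| 0.5 | 0.75 | 53.3 | 0.48 | 90% |
| 0.7 | 0.51 | 78.4 | 0.40 | 97% |

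Wilcoxon power at 0.57 SD is 80% by construction.

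**Step 3: simulation at 40 per arm, 0.57 SD (3,000 runs).** Wilcoxon gave 79 to 80%. ANCOVA gave 80%, 85%, 90% and 97% at ρ of 0, 0.3, 0.5 and 0.7. Rank-ANCOVA gave 78%, 83%, 88% and 95%. A t-test on the simple change score gave 55%, 71%, 83% and 95%. With equal SDs the change has variance 2(1 − ρ), which exceeds that of the 4-week value alone whenever ρ is below 0.5.

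**Step 4: a smaller case, 36 per arm and 0.5 SD (both assumed).** Wilcoxon has about 65% power. ANCOVA has about 70 to 71%, 77 to 78% and 90% at ρ of 0.3, 0.5 and 0.7, and 67 to 68% at ρ of 0 to 0.1. An unadjusted t-test has 67.6%, so about 2 points of the ANCOVA advantage come from assuming normality and not from the pre-dose titre.

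**The case against.** **The other laboratory endpoints.** A reader might infer that every numerical laboratory endpoint is compared without using Day 1. The documents do not support this. Th1/Th17 frequencies, serum biomarkers and T-cell gene expression are endpoints at 1, 2 and 4 weeks with Day 1 samples, so they fall under the GEE sentence. A model of change over time uses Day 1 if Day 1 is an outcome or a covariate. The plan does not say which, nor whether the GEE replaces the Wilcoxon test or supplements it. That is missing detail, not discarded baseline data. The titre, measured twice, could arguably be read as a repeated biomarker too, but it is not named as one and its endpoint is a single time.

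**Validity.** A reader might also infer that a chance baseline imbalance would be mistaken for a drug effect. If half the patients were seropositive at entry (assumed), 40 per arm would differ by five or more seropositive patients in 31.4% of trials. That figure describes binomial scatter. Such scatter is already part of the test's null distribution: simulated under the null with 36 per arm, Wilcoxon rejected 10.2% of the time at the 10% level. Imbalance can move the estimate in one trial; it does not inflate false positives.

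**Size.** The gain rests on an unknown ρ, and the documents suggest reasons why it could be low. Section 5.4 anticipates immune plasma or purified antibodies, which can alter a later titre whatever its starting level. Section 8.1 lets discharged patients be sampled at Day 30 to 60, and up to Day 100. Many pre-dose titres may be undetectable. All of this stands, so the documents do not show that the pre-dose titre explains much of the 4-week titre.

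**Estimand.** The endpoint is a median, which suits a rank test, whereas log-scale ANCOVA estimates a geometric mean ratio. This also stands. It is a reason to keep the medians and to offer rank-ANCOVA.

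**Conclusion.** The point holds for one secondary endpoint, the 4-week IgG titre. A pre-dose value is collected, no adjusted comparison is named, and the natural reading of section 15.1 is an unadjusted Wilcoxon test. The consequence is lost precision: between about 1% and 49% of the variance for ρ from 0.1 to 0.7. At ρ of 0.5, 40 adjusted patients per arm do the work of about 53. These sizes depend on the assumed ρ, normal log titres and the 10% level. The recommendation depends on them less, because adjustment loses essentially nothing when ρ is near zero. For the repeated biomarkers the point is only a request for clarification.

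**What to change.** **Titre.** In section 15.1, name a baseline-adjusted comparison. Suggested wording: *The 4-week log10 IgG titre will be compared between arms by ANCOVA with log10 pre-dose titre and site as covariates, reported as a geometric mean ratio with confidence interval. If many values are below detection, by a criterion fixed before unblinding, rank-ANCOVA will be used instead. Medians by arm and the Wilcoxon test will be reported as descriptive and sensitivity results.* Site is the randomization stratum. Do not substitute a simple change score, which loses power at low ρ.

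**Definitions to settle at the same time.** State which sample is the pre-dose value, since the sections differ between screening and Day 1. State which assay is the endpoint, since section 2 names IgG and section 5.6 neutralizing antibodies. State which sampling days count as 4 weeks.

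**GEE.** State whether Day 1 is an outcome or a covariate, and whether the GEE replaces or supplements the Wilcoxon test.

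**Cost.** The change is to SAP wording only, with no new data. The downside is that two rules are needed: one for a missing pre-dose titre and one for values below detection. The first must be reconciled with the statement in section 15.1 that missing data for secondary endpoints are not imputed, for example by making clear that filling in a baseline covariate is not imputing an outcome.
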